#### **9.4.4 Sensitivity analyses**

Confirmation of the result for the primary efficacy variable will be performed using the per-protocol population without imputation for missing data using the ANCOVA model applied for the primary efficacy analysis.

As another supportive analysis to the primary analysis, the change in LS-BMD Z-score at Month 12 relative to baseline will be compared using the analysis of covariance model with treatment, pooled centers, underlying condition treated with glucocorticoids, baseline LS-BMD Z-score and treatment-by-center interaction as explanatory variables to explore treatment-by-center interactions using the MITT population. If  $p < 0.1000$  for the treatment-by-center interaction test, then, in addition, further work will be done (tabular and/or graphical presentations) as necessary to look for a possible explanation to the differences observed across centers. Tabular and graphical presentations will also be presented as necessary to explain interactions if they exist for underlying condition and baseline pubertal status. Additional prognostic factors will be evaluated as necessary descriptively and in model fitting.

In addition, a responder analysis will be done by comparing the proportion of patients who increase their lumbar spine z-score at Month 12 in the ZOL group relative to the placebo group using the MITT population. Between-treatment differences will be evaluated using a logistic regression model with treatment, pooled centers, underlying condition treated with glucocorticoids and baseline LS-BMD Z-score as explanatory variable.

## **9.5 Analysis of secondary variables**

### **9.5.1 Efficacy variables**

The analyses of secondary efficacy variables will be performed on the MITT population without imputation for missing values unless specified otherwise. Descriptive statistics (mean, median, standard deviation, minimum and maximum) will be presented by treatment group for each continuous variable and the number and percentage of patients will be presented by treatment group for each categorical variable, unless otherwise specified. All hypothesis tests will be evaluated at a 0.05 level of significance, and the p-values will be rounded to the 4th decimal place. Adjustment for multiple comparisons will not be made for any of the secondary efficacy variables since none of these variables is intended to be used for any promotional claims. If changes are made to this plan, appropriate adjustments for multiplicity will be included as part of the report analysis plan (RAP) prior to clinical database lock.

The secondary efficacy variables and their analysis methods are described below.

#### **9.5.1.1 Change in lumbar spine BMD Z-score at Month 6 relative to baseline**

The change in LS-BMD Z-score at Month 6 relative to baseline between zoledronic acid and placebo will be evaluated using an ANCOVA model with treatment, pooled centers, underlying condition treated with glucocorticoids and baseline LS-BMD Z-score as explanatory variables.

#### **9.5.1.2 Change in lumbar spine and total body BMC at Months 6 and 12 relative to baseline**

The change in BMC at the lumbar spine and total body at Month 6 and Month 12 relative to baseline between zoledronic acid and placebo will be evaluated using an ANCOVA model with treatment, pooled centers, underlying condition treated with glucocorticoids and baseline BMC as explanatory variables.

#### **9.5.1.3 Relative change in biochemical markers of bone turnover (Serum NTX, TRAP-5b, BSAP and P1NP)**

A transformation of the log ratio of treatment value vs. baseline value (calculated by dividing the post-baseline value by the baseline value and then applying the  $\log_e$  transformation) at each visit will be used to normalize the distribution of the biochemical marker parameters. An ANCOVA model with treatment group, pooled centers, underlying condition treated with glucocorticoids, and  $\log_e$  (baseline value), as explanatory variables will be performed on the transformed data at each post-baseline time point.

The 2-sided 95% confidence intervals in difference of transformed data between zoledronic acid and placebo will be constructed using the same method as described for the primary analysis based on the described ANCOVA model. In addition, the 2-sided 95% confidence intervals obtained from the model will be back transformed to the original scale.

#### **9.5.1.4 Incidence of new vertebral fractures at Month 12**

The number and percentage of patients with new vertebral fractures at Month 12 will be presented by treatment group. Between-treatment differences will be evaluated using Fisher's exact test.

#### **9.5.1.5 Change in vertebral morphometry at Month 12 relative to baseline**

The change in vertebral morphometry at Month 12 relative to baseline will be evaluated using an ANCOVA model with treatment, pooled centers, underlying condition treated with glucocorticoids and baseline value as explanatory variables

#### **9.5.1.6 Change in metacarpal cortical width at Month 12 relative to baseline**

The change in metacarpal cortical width at Month 12 relative to baseline will be evaluated using an ANCOVA model with treatment, pooled centers, underlying condition treated with glucocorticoids and baseline value as explanatory variables

#### **9.5.1.7 Reduction in pain from baseline**

The reduction in pain from baseline by visit will be evaluated based on whether or not patients have a decrease in their Faces Pain Scale-Revised from baseline. If pain remains the same or worsens from baseline a patient will be classified as '0' and if the pain scale decreased then the patient will be classified as '1'. Whether or not a patient experiences a decrease in pain will be evaluated using a logistic regression model with treatment, pooled centers, underlying condition treated with glucocorticoids and baseline pain score as explanatory variables.

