### 2.2 Secondary objective(s)

1. To evaluate between-treatment differences for the change in LS-BMD Z-score at Month 6 relative to baseline.
2. To evaluate between-treatment differences for the change in LS and total body BMC at 6 and 12 months.
3. To evaluate between-treatment differences for the change in serum P1NP, BSAP, NTX, and TRAP-5b at Month 6 and Month 12 relative to baseline.
4. To evaluate between-treatment differences for the proportion of patients with new vertebral fractures at Month 12 relative to baseline.
5. To evaluate the between-treatment differences for change in vertebral morphometry at Month 12 relative to baseline.
6. To evaluate the between-treatment differences for change in pain using the Faces Pain Scale-Revised (FPS-R) at Months 3, 6, 9 and 12 relative to baseline.
7. To evaluate the between-treatment differences for change in 2nd metacarpal cortical width at Month 12 relative to baseline.
8. To measure urinary concentration of zoledronic acid at Month 12.
9. The safety objective is to demonstrate that zoledronic acid is safe for the treatment of osteoporotic children treated with glucocorticoids through the monitoring of relevant clinical and laboratory safety parameters.

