To evaluate between-treatment differences for the proportion of patients with new vertebral fractures at Month 12 relative to baseline.	Title: Incidence of new vertebral fractures Unit of measure: number and percentage of new vertebral fractures Description: See Section 6.4.1 Time frame: baseline, and 12 months	Section 9.5.1.4
To evaluate the between-treatment differences for change in vertebral morphometry at Month 12 relative to baseline.	Title: Change in vertebral morphometry Description: Quantitative morphometry will be performed by a central reader (see Section 6.4.1 ) Time frame: baseline, and 12 months	Section 9.5.1.5
To evaluate the between-treatment differences for change in pain using the Faces Pain Scale-Revised (FPS-R) at Months 3, 6, 9 and 12 relative to baseline.	Title: Change in pain scale Description: Children will select the face that best fits their pain ( Appendix 4 ) Time frame: baseline, 3, 6, 9 and 12 months	Section 9.5.1.7
To evaluate the between-treatment differences for change in 2nd metacarpal cortical width at Month 12 relative to baseline.	Title: Change in metacarpal cortical width Description: The X-ray Manual provides instructions on the technique. Skeletal bone age will be determined as described in the Imaging Charter Time frame: baseline and 12 months	Section 9.5.1.6
To measure urinary concentration of zoledronic acid at Month 12.	Title: Pharmacokinetics Unit of measure: ng/mL Description: urine will be collected overnight or for at least 4 waking hours from all patients able to provide specimens Time frame: 12 months	Section 9.5.3
The safety objective is to demonstrate that zoledronic acid is safe for the treatment of osteoporotic children treated with glucocorticoids through the monitoring of relevant clinical and laboratory safety parameters	Title: Safety: adverse events, laboratory evaluations and vital signs Description: adverse events will be collected from the first infusion (Visit 2), blood and urine samples, including renal monitoring will be collected (See Section 6.5 ). Also bone safety (change in LS-BMD) is monitored at months 6 and 12. Time frame: baseline through 12 months	Section 9.5.2

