### **4.1 Inclusion criteria**

Patients/ eligible for inclusion in this study must fulfill all of the following criteria:

1. Written informed consent must be obtained before any assessment is performed. An assent needs to be provided in accordance with ICH and local regulations.
2. Children, male or female, between 5 and 17 years of age.
3. A confirmed diagnosis of non-malignant conditions requiring treatment with systemic glucocorticoids (including but not limited to chronic rheumatologic conditions or,

inflammatory bowel disease or Duchenne muscular dystrophy) requiring treatment with systemic glucocorticoids (i.v. or oral) within 12 months prior to screening.

- a. Chronic rheumatologic conditions may include: Juvenile Idiopathic Arthritis (JIA): Systemic onset; JIA: Polyarticular rheumatoid factor positive; JIA: Polyarticular rheumatoid factor negative; JIA: Psoriatic arthritis; JIA: Enthesitis-related arthritis; JIA: Oligoarticular arthritis; JIA: Unclassified; Systemic Lupus Erythematosus (SLE); Juvenile Dermatomyositis; Scleroderma (generalized or localized); Overlap Syndromes (including mixed connective tissue disease); Sjogren's syndrome; Systemic Vasculitis, as defined by the Chapel Hill Consensus Conference on Nomenclature: Giant cell (temporal) arteritis, Takayasu's arteritis, Polyarteritis nodosa, Wegener's granulomatosis, Churg-Strauss syndrome, Microscopic polyangiitis, Essential cryoglobulinemic vasculitis, Cutaneous leukocytoclastic angiitis, Behcet's disease, other vasculitis
  - b. Inflammatory bowel disease may include: Crohn's disease and Ulcerative Colitis
  - c. Duchenne muscular dystrophy
  - d. Nephrotic syndrome who have stable normal renal function for at least 3 months prior to screening
  - e. Other subtypes of secondary osteoporosis in children taking glucocorticoids, except patients with oncologic conditions (such as lymphoma and leukemia) [Appendix 7](#).
4. Lumbar Spine BMD - Z score of -0.5 or worse confirmed by the central imaging vendor.
  5. Evidence of at least 1 vertebral compression fracture of Genant Grade 1 or higher or radiographic signs of vertebral compression fracture seen in X-ray within 1 month of or at screening visit, confirmed by central reading. Radiographic signs of fracture include loss of endplate parallelism, vertebral buckling and endplate interruption.

OR

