### Faces Pain Scale – Revised (FPS-R)

From Pediatric Pain Sourcebook, [www.painsourcebook.ca](http://www.painsourcebook.ca)  
Version: 7 Aug 2007 CL von Baeyer

*In the following instructions, say "hurt" or "pain," whichever seems right for a particular child.*

**"These faces show how much something can hurt. This face [point to left-most face] shows no pain. The faces show more and more pain [point to each from left to right] up to this one [point to right-most face] – it shows very much pain. Point to the face that shows how much you hurt [right now]."**

*Score the chosen face 0, 2, 4, 6, 8, or 10, counting left to right, so '0' = 'no pain' and '10' = 'very much pain.' Do not use words like 'happy' and 'sad'. This scale is intended to measure how children feel inside, not how their face looks.*

0

2

[figure not shown]
4

[figure not shown]
6

[figure not shown]
8

[figure not shown]
10

[figure not shown]

---

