Furthermore, summarizations by ATC class will be provided with regard to a group of specified concomitant medications/significant non-drug therapies, which include osteoporosis-related medications, nutritional supplements, and glucocorticoids. The summary table will be sorted by ATC class in decreasing order of frequency in the zoledronic acid group.

Missing date convention

If the medication start and end dates are recorded in the CRFs, medications that start on or prior to the first infusion in study and end on or after the first infusion in the study including ongoing at end of the study were included in both prior to and after start of study drug administration in the study, respectively.

Partial medication start dates will be imputed as follows:

- Only day is missing: the partial start date will be imputed using 15MONYYYY if the month and year indicate that the medication started prior to the first infusion of study medication or 01MONYYYY if the month and year indicate that the medication started on or after the first infusion of study medication.
- Both day and month are missing: the partial start date will be imputed using 01JULYYYY if the year indicates that the medication started prior to the first infusion of study or 01JANYYYYY if the year indicates that the medication started on or after the first infusion of study medication.

Partial medication end dates will be imputed as follows:

- Only day is missing: the partial end date will be imputed using the last date of the month.
- Both day and month are missing: the partial end date will be imputed as December 31 if the end year is prior to the year of first infusion of study drug or one day after the

last study infusion date if end year is equal to or after the year of first infusion of study drug.

Efficacy evaluation

Analyses of all efficacy endpoints will be performed on the MITT population. Confirmation of the result for the primary efficacy endpoint will be conducted using the PP population without imputation for missing data. All efficacy measurements will be presented in listings.

Analysis for the primary objective

The primary objective is to demonstrate that zoledronic acid administered every 6 months at 0.05 mg/kg (max 5 mg) is superior to placebo for the change in lumbar spine (LS) bone mineral density (BMD) Z-score at Month 12 relative to baseline.

Variable

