The change in vertebral morphometry at Month 12 relative to baseline will be evaluated using an ANCOVA model with treatment, pooled centers, underlying condition treated with glucocorticoids and baseline vertebral morphometry as explanatory variables.

From the model, the treatment difference between zoledronic acid group vs. placebo group will be estimated and presented together with two-sided 95% CI and p-value. In the same table, the LS means and standard errors for change from baseline in vertebral morphometry at Month 12 will be presented for each treatment group. Descriptive statistics will also be shown for baseline and Month 12 visits.

- **Change in 2nd metacarpal cortical width at Month 12 relative to baseline, zoledronic acid group vs. placebo**

The change in 2nd metacarpal cortical width at Month 12 relative to baseline will be evaluated using an ANCOVA model with treatment, pooled centers, underlying condition treated with glucocorticoids and baseline metacarpal cortical width as explanatory variables.

[figure not shown]
From the model, the treatment difference between zoledronic acid group vs. placebo group will be estimated and presented together with two-sided 95% CI and p-value. In the same table, the LS means and standard errors for change from baseline in metacarpal cortical width at Month 12 will be presented for each treatment group. Descriptive statistics will also be shown for baseline and Month 12 visits.

[figure not shown]
- **Reduction in pain from baseline, zoledronic acid group vs. placebo**

Pain is assessed using Faces Pain Scale-Revised (FPS-R) at randomization, Month 3, 6, 9 and 12, which ranges from 0 (No Pain) to 10 (Very Much Pain). Details of FPS-R can be found in Appendix section "Faces Pain Scale – Revised" in the protocol.

The reduction in pain from baseline by visit will be evaluated based on whether or not patients have a decrease in their FPS-R from baseline. If pain remains the same or worsens from

baseline a patient will be classified as '0' and if the pain scale decreased then the patient will be classified as '1'. Whether or not a patient experiences a decrease in pain will be evaluated using a logistic regression model with treatment, pooled centers, underlying condition treated with glucocorticoids and baseline pain score as explanatory variables.

Pharmacokinetic (PK) evaluations

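### Objective 6 asks about change in FPS-R pain, but the only planned test is of any decrease, so children at 0 cannot respond and worsening does not count

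*Protocol*

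**What the plan says.** Protocol section 2.2, objective 6, is to evaluate "between-treatment differences for change in pain using the Faces Pain Scale-Revised (FPS-R) at Months 3, 6, 9 and 12". Table 2-1 titles the endpoint "Change in pain scale" and sends the reader to section 9.5.1.7 for the analysis.

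Section 9.5.1.7 reduces the score to two classes at each visit. A fall from baseline is coded 1. For everything else the rule reads: "If pain remains the same or worsens from baseline a patient will be classified as" 0. The SAP repeats the rule under its heading on reduction in pain and adds: "Whether or not a patient experiences a decrease in pain will be evaluated using a logistic regression model". The covariates are treatment, pooled centers, underlying condition and baseline pain score. Secondary efficacy analyses use the MITT population without imputation.

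Protocol Appendix 4 gives the scoring instruction: "Score the chosen face 0, 2, 4, 6, 8, or 10, counting left to right". The lowest score, 0, means no pain.

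Other pain output is descriptive. The SAP states that "All efficacy measurements will be presented in listings", and both documents promise generic summary statistics by arm for continuous secondary variables.

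**The concern.** The stated objective concerns change in either direction, whereas the tested variable records only whether there was any fall. Two groups of children drop out of the comparison:

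- **Children at 0 at baseline.** They have no lower score to move to, so they are non-responders in both arms at every visit.
- **Children who get worse.** A move from 0 to 10 gets the same code as no change.

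If the arms differ in new or worsening pain at Months 3 to 12, in either direction, the one test attached to objective 6 cannot detect it. Neither document explains why pain is handled this way. The endpoint in the preceding section is analysed as change: "The change in metacarpal cortical width at Month 12 relative to baseline will be evaluated using an ANCOVA model". Vertebral morphometry (9.5.1.5) is handled in the same way.

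**Working it through.** **1. Can a child with no pain enter the analysis?** Yes. Section 4.1 opens its list with "eligible for inclusion in this study must fulfill all of the following criteria", and neither that list nor the exclusions in 4.2 mention pain. The protocol's MITT needs an evaluable baseline for the endpoint, and the SAP's MITT needs LS-BMD Z-scores. Neither depends on the level of pain.

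**2. What the scoring rule implies.** For a child at 0 the response probability is exactly 0. If a share *f* starts at 0, the responder rate in an arm cannot exceed 1 − *f*. With *f* = 50% and 41 per arm, 41 × 0.5 = 20.5, so only about 20 children per arm can respond.

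**3. Where 41 per arm comes from.** The plan's own calculation concerns the primary endpoint (difference 0.63, SD 0.93, two-sided 0.05, 85% power):

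n = 2 × (1.960 + 1.036)² × 0.93² / 0.63² = 39.1, hence 40 per arm, or 80 in total against the stated 82.

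At 41 per arm the t-test power is 85.8%. Allowing for dropout, 41 / 0.9 = 45.6, or 46 per arm as stated. The plan's figure reproduces. No size or power is given for pain.

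**4. Dilution by the floor.** Assume 60% against 30% respond among children with baseline pain. In all children the rates are 0.6(1 − *f*) and 0.3(1 − *f*). With p̄ their mean and n = 41:

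power = Φ{ [|p₁ − p₂| − 1.96√(2p̄(1 − p̄)/n)] / √[(p₁(1 − p₁) + p₂(1 − p₂))/n] }

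- *f* = 0: 60% against 30%, power 79%.
- *f* = 20%: 48% against 24%, power 62%.
- *f* = 50%: 30% against 15%, power 37%. Restricting to the 20 per arm with pain gives 48%.

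This is an unadjusted comparison. The planned model also adjusts for baseline score.

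**5. Planned test against a test of the score.** This is a simulation with assumed inputs. A standard-normal latent baseline is cut into the six FPS-R levels, with share *f* at 0 and the other levels weighted 0.35/0.27/0.19/0.12/0.07. Latent follow-up = ρ × baseline + √(1 − ρ²) × noise − δ if treated, cut at the same points. The base case has ρ = 0.5, δ = 0.6 SD, 41 per arm and 4,000 runs. The planned test is logistic on any decrease with treatment and baseline score, and the comparator is rank ANCOVA. Region and underlying condition were not simulated. In scenario A the drug acts in all children, including preventing new pain. In scenario B it acts only in children with baseline pain.

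| Share at 0 | A: planned | A: rank ANCOVA | A: share kept | B: planned | B: rank ANCOVA | B: share kept |
|---|---|---|---|---|---|---|
| 20% | 53% | 79% | 67% | 52% | 63% | 83% |
| 40% | 37% | 73% | 51% | 38% | 40% | 95% |
| 50% | 29% | 69% | 42% | 29% | 30% | 97% |
| 60% | 19% | 61% | 30% | 19% | 21% | 93% |

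Share kept is planned power divided by rank ANCOVA power, taken before rounding. Ordinary ANCOVA on change gives 80/73/67/60% under A and 66/43/32/22% under B. Type I error is 4.9–5.4% for both tests.

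With δ from 0.4 to 0.8 SD and ρ from 0.3 to 0.7 (2,000 runs each), the share kept at 20% zeros is 56–92% (A) and 77–94% (B). At 50% zeros it is 36–62% (A) and 91–107% (B).

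**6. The contrast that is discarded.** Under A with 50% at 0, 11% worsen on zoledronic acid against 29% on placebo. In a separate simulation the drug only prevents worsening (about 41% worsen on placebo, 16% on active). There the binary comparison rejects about 5% of the time, which is no more than chance, and ANCOVA on change rejects in 33% to 42%.

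**The case against.** The strongest reply concerns weight. A large loss appears only if the drug prevents pain in children who have none. Protocol section 6.4.8 justifies the endpoint by the effect of bisphosphonates on bone and fracture pain, which fits scenario B better, and there the two tests are nearly level once 40% or more start at 0. This stands, and it limits the size of the claim.

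The floor by itself also costs little. When the planned logistic test was restricted to children above 0 under A, power rose from 54% to 56% at 20% zeros, from 38% to 42% at 40% and from 28% to 33% at 50%, with no gain at 60%. Most of the gap under A comes from ignoring worsening. That also stands.

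A responder definition is a recognised choice for a six-level self-report, and it is the same in both documents. Descriptive statistics are planned, and pain reported as an adverse event is tabulated by arm. None of these outputs tests change in FPS-R between arms, which is what objective 6 asks for. Adjusting for baseline score does not help either: a child who cannot respond in either arm carries no treatment information, and no covariate recovers worsening from a code that has dropped it.

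**Conclusion.** The concern holds. The mismatch between objective and test, the impossibility of response at a baseline of 0, and the pooling of worsening with no change all follow from the documents' own rules and need no assumption.

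The power cost does rest on assumptions about the share at 0, the effect and the correlation. It ranges from essentially nothing (effect only on existing pain, 40% or more at 0) to a loss of about half or more of the power (effect in all children, half or more at 0). High correlation softens the latter, with up to 62% kept at 50% zeros. Protocol section 1.1 mentions that nearly half of children with fractures in one body of data had no symptoms. That makes a sizeable share at 0 plausible, but it is not an FPS-R rate for this trial.

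Pain is a secondary endpoint without multiplicity control, the test is valid in size, and the primary conclusion is untouched. The change should be made, but the trial does not depend on it.

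**What to change.** In protocol section 9.5.1.7 and the matching SAP text:

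- Make the test for objective 6 an analysis of the FPS-R score or its change at Months 3, 6, 9 and 12, with treatment, pooled centers, underlying condition and baseline score. Use rank ANCOVA or a proportional-odds model on the six levels, and fix one of them before unblinding.
- Keep the any-decrease responder rate as supportive, restricted to children with baseline FPS-R above 0.
- Tabulate decreased, unchanged and worsened by arm and visit in all children, and show how many were at 0 at baseline.

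The cost is SAP wording, one more model and one table, with no new data. The result is slightly harder to describe than a responder rate, and the gain is small if the drug affects only children who already have pain.
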